8.2. Digits displayed

The number of digits displayed in summary statistics will be increased by one more digit than the captured measurement in the data. The minimum and maximum will be displayed in the same digits as captured in the data.

8.3. Data Handling Convention for Missing Data

In general efficacy data will not be imputed unless otherwise noted. For safety summaries, only observed data will be used unless otherwise specified. Variables type and the corresponding missing data handling are described in section 8.4.

8.4. Analysis Variable Definitions

8.4.1. Study Subjects Measures

8.4.1.1. Protocol Deviation

Protocol deviations will be identified and documented during a data review meeting prior to database lock and confirmed by database lock. The major protocol deviations will be selected in this meeting. At least the following major protocol deviations will include:

- Inclusion/ Exclusion criteria not met
- Test/Procedure performed by non-study trained staff for ALSFRS-R or C-SSRS

‘Inclusion/ Exclusion criteria not met’ will not be summarized because it was confirmed during the data review meeting that this protocol deviation did not occur.

8.4.1.2. Demographic and Other Baseline Characteristics

8.4.1.2.1. Demographics:

Continuous: age, height, weight, Body Mass Index (BMI);

Categorical: age categorized as < 65 years versus \geq 65 years, and \leq 19, 20–29, 30–39, 40–49, 50–59, 60–69, \geq 70, gender, race, country and region defined as North America- NA, Western Europe -WE and Japan - JP

- BMI will be calculated as weight at A03 Baseline (kg) / {height at A01 Screening (m)}² and reported to 1dp.

Table 3: Demographic and Baseline Characteristics¹

| Category | Item | Type of Data | Definition/Breakdown |
|------------|------------------|--------------|--|
| Demography | Gender | Binary | Male, Female |
| | Race | Categorized | 
 1. White 2. Black or African American 3. Asian – Japanese 4. Asian - Not Japanese 5. American Indian or Alaska Native 6. Native Hawaiian or Pacific Islander 7. Not Reported 8. Other |
| | Age (year) | Continuous | |
| | | Categorized | ≤ 19, 20–29, 30–39, 40–49, 50–59, 60–69, ≥ 70 |
| | | Binary | <65, ≥ 65 |
| | Height (cm) | Continuous | |
| | Body weight (kg) | Continuous | |
| | BMI | Continuous | |
| | Country | Categorized | United States, Canada, Germany, France, Italy, Japan |
| | Region | Categorized | 
 1. North America-NA (United States and Canada) 2. Western Europe -WE (Germany, France and Italy) 3. Japan - JP |
| | Ethnicity | Categorized | 
 1. Hispanic or Latino 2. Not Hispanic or Latino 3. Not Reported 4. Unknown |

¹ Baseline characteristics not collected in MT-1186-A03 will be taken from MT-1186-A01

8.4.1.2.2. ALS History²:**Continuous:**

- (1) Disease duration from onset of symptoms to Screening and from ALS diagnosis to A01 Screening (year),
- (2) ALSFRS-R score at A01 Screening

Categorical:

- (3) Disease duration from onset of symptoms to A01 Screening and from ALS diagnosis to A01 Screening categorized at <1 year vs \geq 1 year,
- (4) Initial symptom categorized as 'Bulbar symptom' or 'Limb symptom',
- (5) ALS Diagnosis categorized 'Sporadic' or 'Familial',
- (6) Categorical El Escorial revised Diagnostic,
- (7) Concomitant use of riluzole 'Present' or 'Absent'
(Note: The concomitant riluzole used after the first dose of Study A01 will be included),
- (8) Previous exposure to edaravone before Study A01 'Yes' or 'No'

If the ALS diagnosis date is incomplete, it will be imputed as follows:

- If the ALS diagnosis date is completely missing, the subjects will not be included for the calculation.
- If the start day and month are missing, then the first day of the first month (January) will be used.

Table 4: ALS History Parameters

| Category | Item | Type of Data | Definition/Breakdown |
|---------------------|---|--------------|--|
| ALS Disease History | Disease duration from onset of symptoms to A01 screening (year) | Continuous | (Date of Screening - Date of Onset of Symptoms)/365.25 |
| | | Binary | < 1 year, \geq 1 year |
| | Disease duration from ALS diagnosis to A01 screening (year) | Continuous | (Date of Screening - Date of Diagnosis)/365.25 |
| | | Binary | < 1 year, \geq 1 year |
| | ALSFRS-R score at A01 screening | Continuous | |

² ALS history will be taken from MT-1186-A01

Statistical Analysis Plan
Protocol No. MT-1186-A03

Mitsubishi Tanabe Pharma America, Inc.

| | | | |
|--|--|-------------|--|
| | Initial symptom | Binary | Bulbar symptom, Limb symptom |
| | ALS diagnosis | Binary | Sporadic, Familial |
| | El Escorial revised Airlie House Diagnostic Criteria | Categorized | Clinically Definite ALS, Clinically Probable ALS, Clinically Probable laboratory-supported ALS, or Clinically Possible ALS |
| | Concomitant use of riluzole | Binary | Present, Absent |
| | Previous exposure to edaravone before Study A01 | Binary | Yes, No |

8.4.1.3. Concomitant Medication

Definition of concomitant medications:

At Day 1³, subjects will be asked what medications (including riluzole) they are taking and the information will be recorded in the subject's source documents and eCRF.

Concomitant medication is defined as any medication, other than the study drug, which is taken from first dose date in the MT-1186-A03 study up to week 96 Visit, including prescription, herbal and over-the-counter medications. All concomitant medications taken while the subject is participating in the study will be recorded in the eCRF.

All medications will be classified using the Anatomical Therapeutic Chemical (ATC) classification codes and preferred drug names from the World Health Organization Drug Dictionary (WHO-DD, version from September 2019).

Rules to determine concomitant medications during MT-1186-A03

Medications with start date or stop date on or after the first dose date in the MT-1186-A03 study or ongoing at study week 96 visit will be considered concomitant medications.

If the medication start date is incomplete, then it will be imputed as follows for the purpose of determining concomitant use:

- If the start date is completely missing, the start date will be equal to the date of first dose in the current study. However, if the stop date is not missing and is before the first dose date, then the stop date will be used instead.
- If the start day is missing, the first day of the month will be used.

³ Based upon Week 48 procedures from MT-1186-A01

- If the start day and month are missing, then the first day of the first month (January) will be used.

If the medication stop date is partial, then it will be imputed as follows for the purpose of determining concomitant use:

- If the stop date is completely missing and the medication is not ongoing, the stop date will be equal to the last study drug dose date or date of completion /withdrawal, whichever is the latest.
- If the stop day is missing, the last day of the month will be used.
- If the stop day and month are missing, then the last day of the last month (December) will be used.

8.4.1.4. Exposure to Study Medication and Compliance

Exposure

Study medication exposure in days during MT-1186-A03 will be calculated for each subject using the following:

Actual exposure duration (days)

$$= \sum_{i=1}^{24} (\#count of planned study medication dosing days in cycle i - \#count of study medication days missed in cycle i + \#count of additional study medication days taken in cycle i)$$

The #count of planned study medication dosing is 10 in cycle 1 to 24.

The #count of study medication missed and additional study medication are collected by CRF visit.

The cycle will be automatically calculated using the date of the first dose in MT-1186-A03.

The total exposure in person years will be calculated as the sum of duration of exposure to study treatment over all patients in days divided by 365.25.

Treatment Compliance

Treatment compliance during MT-1186-A03 will be calculated for each subject using the following:

Treatment compliance(%)

$$= \frac{\text{Actual exposure duration}}{\sum_{i=1}^{24} (\#count of planned study medication dosing days in cycle i)} \times 100\%$$

Treatment compliance will be calculated using the formula above and reported to 1dp.

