9.3.1. Adverse Events

AEs that occurred on or after the first dose in the MT-1186-A03 will be summarized, which implies AE that occurred during MT-1186-A01 will not be summarized.

The following summaries will be provided:

- A Summary table of the overall incidence (number and percentage) and the number of events will be provided for TEAE, TEAE related to study drug, severe TEAEs, TESAEs, TEAEs leading to study treatment discontinuation and TEAEs leading to death.

The numbers and proportions of subjects will be calculated for the following:

- TEAEs by SOC and PT
- TEAEs by SOC, PT and severity
- Most Common ($\geq 5\%$ of patients) TEAEs by SOC and PT
- TEAEs related to study drug by SOC and PT
- TEAEs related to study drug by SOC, PT and severity
- TESAEs by SOC and PT
- TESAEs related to study drug by SOC and PT
- Severe TEAEs by SOC and PT
- Severe TEAEs related to study drug by SOC and PT
- TEAEs leading to study treatment discontinuation by SOC and PT
- TEAEs by SOC, PT and relationship to study drug
- TESAEs by SOC, PT and relationship to study drug
- TEAEs leading to death by SOC and PT

For these tables, SOC will be sorted by International Agreed Order; then within SOC, PT will be sorted by PT code.

The following summaries will be provided:

- A Summary table of the overall incidence (number and percentage) will be provided for Peripheral Neuropathy Standardized MedDRA query (SMQ) TEAEs

The numbers and proportions of subjects will be calculated for the following:

- TEAEs of Peripheral Neuropathy SMQ by SOC and PT
- Serious TEAEs of Peripheral Neuropathy SMQ by SOC and PT

TEAEs by Oral/PEG subgroup, SOC and PT

The numbers and proportions of subjects with TEAEs and event rate of TEAEs will be calculated by Oral/PEG subgroup, SOC and PT. The event rate of TEAEs will be calculated as the number of TEAEs divided by total exposure to investigational product by Oral/PEG dosing and expressed as 100 person years. Any TEAE occurred after subject switched to PEG will be classified under the PEG subgroup.

The exposure (in days) under Oral in cycle switched to PEG will be calculated as difference: Oral days=PEG switch Date during MT-1186-A01 or MT-1186-A03 - Cycle first date. If Oral days is less than 0 then Oral days will be 0.

The oral days does not exceed actual exposure duration (days) in the cycle. The exposure under PEG will be calculated as difference:

PEG days= actual exposure duration - Oral days.

TEAEs by Cycle

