The numbers and proportions of subjects with TEAEs will be calculated by Cycle of treatment and by SOC and PT. Cycles will be categorized into grouping of: Cycle 1-6, Cycle 7-12, Cycle 13-18 and Cycle 19-24.

For each of the summaries, multiple occurrences of the same event within a subject will be counted once in the summaries by SOC and PT; multiple occurrences of the same event within a subject will be counted once in the maximum severity category (severe > moderate > mild) and/or maximum study drug relationship category (reasonable possibility / no reasonable possibility). If severity or relationship is found to be missing the most severe occurrence will be imputed for that particular summary.

In the analysis of TEAEs by Cycle, reoccurrences of TEAE's per subject can be shown multiple times if occurred in different cycles categories. The TEAEs occurred at follow up period of subjects who completed the study will be categorized Cycle 19-24.

Subject's data listings will be provided for: TEAEs, TESAEs, TEAE leading to discontinuation of study drug and Death

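### SAP person-years count only dosing days (10 in 28) while TEAEs count on all days, and the 24-cycle exposure and compliance sums state no stop for subjects who leave

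*SAP*

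**What the plan says.** SAP 8.4.1.4 defines actual exposure duration as a sum over cycles 1 to 24 of planned dosing days, minus missed days, plus additional days. The planned count is fixed: "The #count of planned study medication dosing is 10 in cycle 1 to 24". Total person-years are "calculated as the sum of duration of exposure to study treatment over all patients in days divided by 365.25". Compliance is actual exposure divided by the planned days summed over the same 24 cycles. SAP 9.1.6 lists the person-years total as an output.

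SAP 9.3.1 plans one table of rates per 100 person-years, by Oral/PEG: "The event rate of TEAEs will be calculated as the number of TEAEs divided by total exposure to investigational product by Oral/PEG dosing". The numerator is wide: "AEs that occurred on or after the first dose in the MT-1186-A03 will be summarized", with no exclusion of drug-free days. In the cycle where a subject switches, "Oral days=PEG switch Date during MT-1186-A01 or MT-1186-A03 - Cycle first date", with the limit that "The oral days does not exceed actual exposure duration (days) in the cycle". PEG takes what is left: "PEG days= actual exposure duration - Oral days".

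Protocol 17.2.3 defines exposure differently, as the calendar span from first to last dose, ignoring interruptions. SAP Section 11 lists only the physical examination change as a departure from the protocol.

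**The concern.** A rate per 100 person-years needs events and time taken from the same period. Here the events come from all 28 days of each cycle and the time from only the 10 dosing days. The study's primary objective is long-term safety, and most readers would take the rates and the person-years total as calendar-time figures and compare them with calendar-time figures elsewhere.

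The second problem is independent of the first. Subjects can leave before cycle 24 through withdrawal (protocol 9.6) or because the drug becomes commercially available (protocol 10.1.2). Both sums still run over all 24 cycles, and no sentence ends them. A leaver's exposure and compliance then depend on a programming or data-entry choice that the SAP does not make.

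**Working it through.** **Inputs.** Cycle length 28 days (SAP 4.1); 10 planned dosing days in each of 24 cycles (SAP 8.4.1.4); divisor 365.25 (SAP 8.4.1.4); approximately 140 subjects (SAP 4.2), used only for scale; non-compliance limits of 80% and 120% (SAP 9.1.6, protocol 14.3).

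**Plan's own figures.** 24 × 28 = 672 days, and 672/7 = 96 weeks, as in SAP 10.2. Cycle 24 starts on day 23 × 28 + 1 = 645, as in SAP 8.6.

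**Person-years for a fully adherent completer**
- SAP basis: 24 × 10 = 240 days; 240/365.25 = 0.657.
- Calendar time: 672/365.25 = 1.840. Factor 672/240 = 2.80.
- Protocol 17.2.3 span, last dose on day 10 to 14 of cycle 24: 654 to 658 days; 654/240 = 2.73 and 658/240 = 2.74.
- One TEAE per completer: 100/0.657 = 152 per 100 person-years, against 100/1.840 = 54.
- 140 such completers: 140 × 240/365.25 = 92.0, against 140 × 672/365.25 = 257.6.
- If 80% or 120% of doses are taken, the factor is 672/192 = 3.50 or 672/288 = 2.33.

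**Switch cycle.** Assume the 10 doses fall on cycle days 1 to 10 and all are taken. A switch on day d gives Oral min(d − 1, 10) days and PEG the rest of the 10. From d = 11 onward PEG gets 0 days, while TEAEs after the switch count as PEG. For the effect on the rate table, assume also that d is uniform over 1 to 28, that cycles after exit add no days, and that the Oral row consists of never-switchers (factor 2.80). The mean PEG time in the switch cycle is then 406/28 = 14.5 calendar days and 55/28 = 1.96 credited days.
- 3 further cycles: (14.5 + 84)/(1.96 + 30) = 3.08; 3.08/2.80 = 1.10.
- 6 further cycles: (14.5 + 168)/(1.96 + 60) = 2.95; 2.95/2.80 = 1.05.
- 18 further cycles: (14.5 + 504)/(1.96 + 180) = 2.85; 2.85/2.80 = 1.02.

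**Leavers.** Take an adherent subject who leaves after cycle 12 (assumption).
- Later cycles not entered as missed: 24 × 10 = 240 days, 100% compliance.
- Later cycles entered as missed: 120 days, 120/240 = 50%.
- Both sums ended at exit: 120 days, 120/120 = 100%.

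Where the numerator stops at exit and the denominator stays at 240, an adherent leaver after 19 cycles shows 190/240 = 79.2% and after 20 cycles 200/240 = 83.3%. Leaving after 19 or fewer cycles therefore reads as non-compliance.

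Crediting cycles after exit works against the dosing-day inflation. With a share p leaving after cycle 12 (assumption), the net factor is (672(1 − p) + 336p)/240, which is 2.52 at 20%, 2.24 at 40% and 1.96 at 60%.

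**The case against.** The best defence is that the SAP openly defines a dosing-day scale, and nothing on that scale is miscalculated. The figure 2.80 is relative to calendar time, so a footnote might be enough. It stands that the definition is explicit and that dosing days are a legitimate summary under their own name. But a footnote would leave a rate whose events and time cover different days, under a label that says person-years.

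The reach is also narrow, and this stands. The documents plan one rate table and one person-years total, the other TEAE tables are counts and percentages of subjects, and no hypothesis is tested. A reader might infer that the 2.80 carries into the PEG:Oral comparison. It does not, because it is largely common to both rows. The switch-cycle rule is mostly the same unit mismatch: on a dosing-day scale, zero PEG days is right once that cycle's doses are finished.

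A reader might go further and infer that leavers will be credited with 240 days, so that PEG rates come out far too low relative to Oral. The documents do not support this. The quantity is called actual exposure and is reported by cycle, which points away from crediting cycles never entered. Recording of missed days after exit depends on the CRF, and any effect on the table depends on exit patterns that the documents do not give. Likewise, the references to evaluation periods in SAP 9.1.6 and to visit-to-visit assessment in protocol 14.3 sit badly with the 50% compliance reading. These are hints and not rules, because SAP 9.1.6 sends the calculation back to 8.4.1.4.

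The sentence "The TEAEs occurred at follow up period of subjects who completed the study will be categorized Cycle 19-24" governs the by-cycle table. It shows that follow-up events can be TEAEs, but it is only indirect support for the rate numerator.

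**Conclusion.** The point holds. As written, the SAP gives person-years and rates per 100 person-years that are not on a person-time scale. The factor of 2.80 needs only full adherence and completion. It is 2.73 to 2.74 against the protocol's own span, and with leavers it depends on how their later cycles are handled. The switch-cycle rule adds a modest shift in the PEG:Oral ratio, about 1.02 to 1.10 times under the assumptions shown. The missing stop is a gap in specification: the documents do not show which reading will be programmed, only that the choice can double a mid-study leaver's exposure or halve that subject's compliance. The n (%) TEAE tables are not affected. This should be fixed before database lock.

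**What to change.** - (a) For person-years and TEAE rates, use calendar time at risk from the first A03 dose to the end of the subject's TEAE counting period, and state that end. Split both events and time at the PEG/RIG switch date.
- (b) Report dosing days separately, under that name.
- (c) End both the exposure sum and the compliance denominator at the recorded treatment discontinuation or completion date. Do not use the last dose, because doses missed before stopping would then drop out and poor adherence could read as 100%. For the exit cycle, the planned count should be the doses scheduled up to that date. The SAP gives only a count of 10 per cycle, so it must state how that schedule is derived.
- (d) List the departure from protocol 17.2.3 in SAP Section 11. This is documentation only, since SAP Section 2 says that the SAP supersedes the protocol on statistical details.

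The cost is SAP wording and a small reprogramming step. The SAP already uses the first dose date, the switch date and the completion or withdrawal date. If the CRF holds no separate treatment-stop date, the SAP must name the date that stands in for it. The downside is that rates will not match any earlier output on the dosing-day basis. Total dosing days will also be lower if leavers would otherwise have been credited with all 24 cycles.

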## **9.6 Withdrawal of Individual Subjects**

A subject will be withdrawn from the study if the subject meets any of the following criteria:

- Requests to be withdrawn from the study;
- Has been found to be ineligible for participation in the study;
- The investigator (or subinvestigator) concludes that a subject should be withdrawn if continuation in the study is difficult due to AEs (e.g., hypersensitivity reactions);
- Is pregnant;
- Requires tracheostomy;
- Requires permanent assisted mechanical ventilation ( $\geq 23$  hours/day);
- The investigator (or subinvestigator) judges' continuation of the study to be inappropriate due to exacerbation of the primary disease;
- Development of significant liver dysfunction:
  - ALT or AST greater than 8 times the ULN;
  - Persistent ALT or AST of greater than 5 times the ULN for at least 2 weeks;
  - ALT or AST greater than 3 times the ULN AND elevated total bilirubin greater than 2 times ULN;
  - Symptoms consistent with liver dysfunction (e.g., fatigue, nausea, vomiting, abdominal pain/tenderness, fever, rash, eosinophilia  $>5\%$ ) with concomitant ALT or AST greater than 3 times the ULN.
- Note: Subjects meeting these criteria do not require withdrawal if alternative etiology is identified on discussion with the Study Medical Monitor.
- Noncompliance (i.e., misses more than 20% of doses in 2 consecutive dosing cycles, after consultation with MTDA or designee).

If a subject is withdrawn prematurely from the study, the date the subject is withdrawn from the study and the reason for withdrawal will be recorded in the electronic case report form (eCRF).

In the event that a subject drops out of the study at any time, the reason for discontinuation must be fully documented in the source documents and the eCRF. The Investigator site personnel will document the AEs and any other assessments in the source documents and will make every effort to complete all required early termination (ET) assessments. Study sites must make all efforts to follow-up with phone calls.

Subjects who are withdrawn from the study following enrollment may not re-enter the study.

The study may be terminated by the Sponsor at any time upon becoming aware of data that could compromise the safety and/or well-being of subjects or for any other reason it deems appropriate.

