#### **10.1.2 End of Treatment**

The EOT visit will occur at Week 94, when the drug is commercially available in that country, or in the event the Sponsor discontinues the study.

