#### **14.3 Treatment Compliance**

The prescribed dosage, timing, and mode of administration of study medication may not be changed except for PEG/RIG dosing as the subject's disease progresses. Drug compliance should be assessed on a per cycle basis by site staff either via phone calls or during their on-site study visits to assess their dosing compliance. Subjects will be asked questions regarding the compliance, and any departures from the intended regimen must be recorded in the eCRF. Study drug accountability and treatment compliance will be documented throughout the study period.

Subjects will be asked to return all unused medication including empty and partially used medication. Study medication dispensed at the previous visit will be collected by the site and compliance will be assessed by counting the returned study medication bottles.

Non-compliance is defined as taking <80% or >120% of study medication during evaluation periods (visit to visit).

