9.1.6. Study Medication Exposure and Compliance

Study medication exposure during MT-1186-A03 will be calculated as specified in section 8.4.1.4. The following information will be summarized and listed for the safety analysis population:

- The number of subjects exposed to study treatment
- The number of subjects exposed to study treatment by oral administration
- The number of subjects exposed to study treatment by PEG/RIG administration
- Duration of exposure of study treatment (days) by Cycle and Total
- Total duration of exposure to study treatment, expressed as person years (sum of exposure to study treatment)
- Total duration of exposure (days) under PEG/RIG administration
- Time to date subjects switched to PEG/RIG administration

Treatment compliance will be determined by performing study treatment accountability of returned study treatment used and unused according to section 8.4.1.4. Treatment compliance will be summarized and listed for the safety analysis population using descriptive statistics. Non-compliance is defined as taking $< 80\%$ or $> 120\%$ of study medication during evaluation periods. The proportions of subjects with non-compliance as defined above will be summarized and listed for the safety analysis population.

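### The compliance denominator in SAP 8.4.1.4 is 240 planned days for every subject, with no stop when treatment ends early

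*SAP*

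**What the plan says.** SAP 8.4.1.4 defines actual exposure, for each subject, as a sum over cycles 1 to 24 of planned dosing days, minus missed days, plus additional days. Compliance is that sum divided by planned days over the same 24 cycles. The planned count is a constant: "The #count of planned study medication dosing is 10 in cycle 1 to 24". The other two terms come from the CRF: "The #count of study medication missed and additional study medication are collected by CRF visit". Neither sum is limited to the cycles a subject received.

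SAP 9.1.6 points back to this formula ("Treatment compliance will be determined by performing study treatment accountability of returned study treatment used and unused according to section 8.4.1.4") and adds the <80% or >120% definition of non-compliance. It then requires a table: "The proportions of subjects with non-compliance as defined above will be summarized and listed for the safety analysis population". Protocol 14.3 sets the same limits period by period: "Non-compliance is defined as taking <80% or >120% of study medication during evaluation periods (visit to visit").

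Treatment can end before cycle 24 in several foreseen ways. Protocol 10.1.2 states: "The EOT visit will occur at Week 94, when the drug is commercially available in that country". Protocol 9.6 withdraws subjects who need tracheostomy or permanent ventilation, and those for whom the investigator judges "continuation of the study to be inappropriate due to exacerbation of the primary disease".

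**The concern.** A compliance percentage should compare doses taken with doses due while the subject was on treatment. With 240 as a constant denominator, the doses due do not depend on how long the subject was treated. Leaving early is then mixed with poor adherence, or poor adherence before leaving is hidden. Which of the two happens depends on what the numerator holds for cycles after exit, and the SAP is silent on that.

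Exit at commercial availability has nothing to do with adherence, and exit for progression is to be expected in ALS. At stake are the compliance summary and, depending on how the threshold is applied, the proportion of subjects called non-compliant. Both help to show how much drug the long-term safety evidence rests on.

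**Working it through.** **Inputs.** 10 planned days per cycle and 24 cycles (SAP 8.4.1.4); 28-day cycles (SAP 8.6, Table 6); limits of 80% and 120% (SAP 9.1.6, protocol 14.3); about 140 subjects (SAP 4.2), used only for illustration. The documents give no dropout rate.

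**The plan's own figures.** 24 × 28 / 7 = 96 weeks, as in SAP 10.2. Cycle 24 starts on Day 23 × 28 + 1 = 645, as in Table 6. Its first 14 days end on Day 658, which is Week 94, as in protocol 10.1.2. So 24 × 10 = 240 is the correct denominator for a subject who completes.

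**Formulas.** Let k be the number of whole cycles treated and m the net missed days (missed minus additional) in them.

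- On-treatment compliance: (10k − m) / 10k.
- Reading 1, post-exit days drop out of the numerator or count as missed: (10k − m) / 240.
- Reading 2, post-exit missed days taken as 0: (240 − m) / 240.

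| Subject | On treatment | Reading 1 | Reading 2 |
|---|---|---|---|
| k = 6, m = 0 | 60/60 = 100% | 60/240 = 25.0% | 240/240 = 100% |
| k = 12, m = 0 | 120/120 = 100% | 120/240 = 50.0% | 240/240 = 100% |
| k = 19, m = 0 | 190/190 = 100% | 190/240 = 79.2% | 240/240 = 100% |
| k = 20, m = 0 | 200/200 = 100% | 200/240 = 83.3% | 240/240 = 100% |
| k = 6, m = 18 | 42/60 = 70.0% | 42/240 = 17.5% | 222/240 = 92.5% |
| k = 12, m = 36 | 84/120 = 70.0% | 84/240 = 35.0% | 204/240 = 85.0% |

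For k = 24 all three formulas agree.

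**Threshold.** 80% of 240 is 192 days. If the limit is applied to the overall percentage, Reading 1 flags every fully adherent subject who leaves after 19 or fewer cycles. If it is applied visit to visit, periods before exit are unaffected.

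**Exposure.** Under Reading 1 exposure is 10k − m, which is right. Under Reading 2 it is 240 − m: a fully adherent exit after cycle 6 is credited with 240 days instead of 60. SAP 9.3.1 takes PEG days as exposure minus oral days. For a switch on the first day of cycle 5 and exit after cycle 6, PEG days become 240 − 40 = 200 instead of 60 − 40 = 20, which lowers the PEG event rate.

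**Cohort illustration.** Assumptions, not from the documents: all subjects fully adherent, a share c completes, and exits are uniform over cycles 1 to 23 (mean 120 days, mean 50.0% under Reading 1).

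| c | Mean compliance, Reading 1: 100c + 50(1 − c) | Below 80%, Reading 1: (1 − c) × 19/23 | True person-years: 140 × (240c + 120(1 − c)) / 365.25 |
|---|---|---|---|
| 0.7 | 85.0% | 24.8% | 78.2 |
| 0.5 | 75.0% | 41.3% | 69.0 |
| 0.3 | 65.0% | 57.8% | 59.8 |

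Under Reading 2 this adherent cohort shows no compliance error, but person-years would be 140 × 240 / 365.25 = 92.0 in every row.

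**The case against.** The strongest reply is that the 24 is only a maximum. Missed and additional days come from CRF visits, and compliance rests on returned drug, so cycles after exit have no record. A programmer would naturally sum only cycles with records, above and below the line. SAP 8.3 can be cited in support: "For safety summaries, only observed data will be used unless otherwise specified". That practice would largely avoid the error, and it may be what is done; the CRF is not among the documents. But planned days are a stated constant, not an observation, so SAP 8.3 does not shorten the denominator. Summing recorded cycles departs from the written formula and leaves the final part-cycle undefined. The protocol's exposure formula (17.2.3) does stop at the last dose, but SAP Section 2 says that the SAP supersedes the protocol's analysis text.

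Two stronger readings are tempting and are not supported. A reader might infer that compliance is wrong for every early leaver; under Reading 2, a leaver with no net missed or extra days gets a correct 100%. A reader might also infer that exposure and the event rates are overstated. That needs Reading 2, which credits dosing days after exit to a quantity called actual exposure and tabulated by cycle, where they would be easy to see. It is possible on the text, but the less likely coding.

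It also stands that compliance is not an endpoint, that SAP 7.2 plans no formal testing, and that adverse event tables counting subjects do not use exposure.

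**Conclusion.** Wrong as written; minor to should-fix. The 240-day denominator follows directly from SAP 8.4.1.4, and no other section shortens it. The likelier consequence is understated compliance for leavers: 25.0% or 50.0% for a fully adherent stop after cycle 6 or 12. The less likely one is masked non-adherence (92.5% for a true 70.0%), together with inflated exposure, person-years and Oral/PEG denominators.

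The proportion of non-compliant subjects is affected only if the threshold is applied to the overall percentage. SAP 9.1.6 leaves this open by dropping the protocol's visit-to-visit wording. The per-subject figures are exact arithmetic under the stated reading; the cohort figures rest on assumed completion and exit times. Confidence is high that the stopping rule is missing, and lower on which consequence would appear, because that depends on the CRF and the programming.

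**What to change.** In both sums, replace the upper limit 24 with the subject's last countable cycle:

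- Count every Table 6 cycle that ended before the recorded treatment discontinuation or completion date.
- Count the cycle containing that date only if a dose was taken in it, or if its 14-day dosing period had already ended by that date.
- Count no later cycle.
- Enter untaken planned days of counted cycles as missed, and credit no exposure after the last dose.

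Checks, with all earlier doses taken:

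- Stop on Day 88 without a cycle 4 dose (cycle 4 starts on Day 85, and visits have a ±7-day window): 30/30.
- Stop on Days 169–176 without a cycle 7 dose: 60/60.
- Last dose in cycle 4, discontinued at the end of cycle 6: 40/60 = 66.7%, so doses missed before discontinuation still count.
- Completers are unchanged.

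Use the same limit for by-cycle exposure, person-years and the Oral/PEG split. Apply the <80%/>120% threshold visit to visit as in protocol 14.3, or state otherwise.

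The cost is SAP wording and one programming change, with three downsides. First, a mid-cycle exit after at least one dose is charged up to 9 untaken days. With one dose in cycle k + 1 the result is (10k + 1)/(10k + 10): 31/40 = 77.5% in cycle 4, lower in cycles 1 to 3, and 41/50 = 82.0% in cycle 5. Second, doses missed in a final cycle that has no dose and is left during its dosing period are not charged. Third, protocol 9.6 records the withdrawal date, but whether a separate treatment discontinuation date exists must be checked on the CRF.
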